#### 14.2.3 CLASSIFICATION OF AN ADVERSE EVENT

The following categories will be used to classify AE in the protocol.

- **Mild** – Events that will require minimal or no treatment intervention and does not interfere with the participant's daily activities.
- **Moderate** – Events that could result in a low-level inconvenience or concern with the prescribed therapeutic measures. A moderate event may cause interference with normal functioning.
- **Severe** – Events that can interrupt a study participant's typical daily activity and would require systemic drug therapy or another intervention/treatment. Severe events can pose as potentially life-threatening or incapacitating. Note, the terms severe and serious are not necessarily equal.

Relatedness: AEs that result from the presence, application, or performance of the remotely administered exercise regimen will be considered system related. AEs that are not temporally related, that affect organ systems or body-sites that are not affected by the exercise regimen, or that can be attributed to another cause will be considered unrelated.

Adverse Event relationships to the study intervention will be classified as either related to study participation or not related to study participation. Expected and unexpected AEs will be clearly delineated from one another. Expected AEs include worsening HF symptoms, orthopedic injury (including fracture, sprain, or tear of bone or soft tissue), myocardial infarction, serious arrhythmia, and ICD therapy. All other AEs will be considered unexpected.

#### 14.2.4 ADVERSE EVENT REPORTING

Timely, accurate, and complete reporting and analysis of safety information for clinical studies are crucial for the protection of subjects. Reporting and analysis of safety data are mandated by regulatory authorities worldwide. AE CRF's will be collected for all AEs that are potentially study-related and all serious AEs regardless of their relationship to the study. For AEs that require immediate reporting, initial reporting may be done by phone, fax, email or on the CRF completing as much information as possible. The AE CRF must be completed as soon as possible. For any changes in status of a previously reported adverse event (i.e. change in actions taken, change in outcome, change in relatedness), an update to the original AE must be completed. All reported AEs must be followed until the AE has been resolved, is unresolved with no further actions planned, the subject dies or exits the study, or until study closure, whichever occurs first. In the event that a subject is exited from the study prior to study closure, all efforts should be made to continue following the subject until all unresolved system related AEs, as classified by the investigator, are resolved or they are unresolved with no further actions planned. At the time of study exit, all collected AEs with an outcome of "Unresolved, further actions or treatment planned" must be reviewed and an update to the original AE must be reported. At a minimum, if there are no changes to the description, relatedness, test and procedures or actions taken, the outcome must be updated to reflect "Unresolved at time of study closure."

All AEs will be reported to the sponsor and the IRB within 10 working days of the event.

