## 9 STUDY OUTCOMES

### 9.1 AIMS

**Aim 1:** Compare the mean Abbott ICD and CRT-D device measured daily PA obtained over the 1 week before randomization (baseline) and 12 weeks after randomization among patients randomized to remote CR versus usual management. This objective was chosen to determine if it is possible to objectively measure a clinically meaningful change in PA using an ICD or CRT-D device. Further, the primary objective assesses whether a remotely administered exercise training program can increase the observed PA over a relatively short time interval.

**Aim 2:** Compare baseline and 12 week Kansas City Cardiomyopathy Questionnaire (KCCQ) HF symptom severity scores among patients randomized to remote CR versus usual management. This objective was chosen to determine if the remotely administered exercise training is associated with subjective improvement in HF symptoms. This endpoint has been used previously in studies of exercise training in patients with HF, so we should be able to compare the direction and magnitude in change in our study to results obtained in prior studies.

**Aim 3:** (Safety) Report Adverse Events of heart failure hospitalization, fracture, myocardial infarction, serious adverse arrhythmia, and ICD therapy among patients randomized to remote CR versus usual management. This objective is important since little data are available regarding the safety of starting an exercise training program without a prior CPET study. We will determine if patients randomized to exercise training experience excess risk.

**Aim 4:** Measure the correlation between change in daily PA measured by the Abbott ICD or CRT-D device between baseline and end of follow up and change in KCCQ HF symptoms severity score measured between baseline and end of follow up. This objective will allow us to determine what change in device measured PA is associated with an improvement in QOL.

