## 10 DATA QUALITY

## 10.1 DATA COLLECTION PROCEDURES AND DATA ELEMENTS

Data will be extracted from the implanted ICD or CRT-D device. Patient-reported outcomes (PROs) will be collected via the Pattern Health smartphone App. Patients will report study-related AEs through the App. Any reported AEs will be followed up with a phone call and screening in the EMR. At study conclusion, the EMR will also be screened for any unreported AEs.

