### 10.1.1 PATIENT REPORTED DATA AND DEVICE DATA

Patient reported data collected via the Pattern Health Patient App include weight, questionnaire responses, blood pressure and blood sugar, review of current medications, recent hospitalization and the presence of symptoms (shortness of breath or chest pain).

Devices used in this study will be integrated with the Pattern Health App and the data collected will be passively uploaded to the Duke EMR.

Device data for this study include:

- Abbott Medical ICD or CRT-D implantable device: heart rate, daily physical activity, physical activity intensity, and heart failure severity

All AEs will be gathered electronically through the Pattern health smartphone application. The study coordinator will request addition information through the App on an individual basis. In the event that a subject fails to respond to requests for data through the App, a follow-up telephone call will be placed by a study coordinator. All AEs will be recorded in the eCRF.

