### 10.1.2 DUKE EPIC EMR

The Duke EMR will be used to collect the results of recent testing (echocardiograms, ECGs) and will be used to ascertain if the patient has experienced any study related adverse events.

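### The protocol contradicts itself on whether non-serious adverse events are recorded regardless of relatedness, so some Aim 3 events could be captured unequally by arm

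*Protocol*

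**What the plan says.** Protocol section 9.1 gives the purpose of Aim 3: "We will determine if patients randomized to exercise training experience excess risk". Section 9.2.3 names five events of special interest: HF admission, MI, fracture, serious arrhythmia and ICD therapy. The planned output (S2 in protocol section 11.8.2 and SAP sections 6.4 and 7) is a listing, with no test or rate comparison.

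Two sets of statements govern what is recorded.

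- **With a relatedness limit.** Section 14.2.4: "AE CRF's will be collected for all AEs that are potentially study-related and all serious AEs regardless of their relationship to the study". Section 10.1: "Patients will report study-related AEs through the App". Section 10.1.2 says the EMR "will be used to ascertain if the patient has experienced any study related adverse events", and section 5.5 describes EMR use in the same terms.
- **Without one.** Section 10.1.1: "All AEs will be recorded in the eCRF". Section 7.6 has any AE self-reported. Section 10.1 ends with an EMR screen at study conclusion for AEs that were not reported. Section 12.5 names the sources for the safety endpoint (App questionnaires, EMR, device electrograms) with no condition on relatedness or arm. The last line of section 14.2.4 sends all AEs to the sponsor and the IRB.

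Relatedness is set out in section 14.2.3. It begins: "AEs that result from the presence, application, or performance of the remotely administered exercise regimen will be considered system related". Events with no temporal link, events in body sites that the regimen does not affect, "or that can be attributed to another cause will be considered unrelated". A later sentence has events "classified as either related to study participation or not related to study participation".

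**The concern.** A safety comparison needs events to be ascertained in the same way in both arms. A form rule that depends on relatedness to an intervention given in only one arm does not guarantee that. Usual-care patients have no exercise regimen, so a non-serious event there can hardly result from it. In the CR arm the same event passes or fails by a judgement made with the assignment known (section 4.3), and it can fail because another cause is available, which is common in patients with HF and an ICD.

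If capture is lower in usual care, equal true rates look like excess risk with exercise. If CR-arm events are attributed to underlying disease, a real excess can shrink or vanish. Because S2 is only a listing, collection determines the whole safety result, and no later analysis recovers an unrecorded event. Section 10.3 convenes no DSMB, section 6.4 makes AE occurrence the trigger for discontinuing the intervention, and section 9.1 says the results will inform a pivotal trial.

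**Working it through.** The plan states no AE rate, capture rate, safety margin or safety power, so there is no figure to reproduce. The check is mainly textual.

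**1. Which events does the section 14.2.4 form rule leave out?** A form is required if an event is serious or potentially study-related. An event is exposed only if it is both non-serious and not judged potentially related.

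**2. Which of the five can be non-serious?** Against section 14.2.2:

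| Event | Position |
|---|---|
| HF admission | Serious by definition |
| Serious arrhythmia | Serious by its label, though section 9.2.3 gives no definition |
| MI | Usually serious, through admission or threat to life |
| Fracture | Can be non-serious if not admitted |
| ICD therapy | Can be non-serious if not admitted |

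The exposed set is therefore mainly fracture and ICD therapy without admission. Section 14.2.3 lists both among expected AEs.

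**3. Can a usual-care event count as related?** Under the regimen wording, hardly ever. Under the study-participation wording, possibly: section 8.4.2 gives those patients the App and a Garmin too. That sentence, however, opens by referring to the relationship to the study intervention, so it does not clearly settle the matter.

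**4. Do other statements close the gap?** Sections 7.6, 10.1.1 and 12.5, the final EMR screen in 10.1 and the last line of 14.2.4 would close it if followed. No section says which rule prevails. Section 12.5 names sources but does not say that an event found there goes on an AE form.

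**5. Illustration (all rates assumed).** Let n = 25 per arm (50 subjects, 1:1), p = true 12-week risk of a non-serious event of interest, equal in both arms, and c = fraction of usual-care events recorded, with all CR events recorded.

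- Expected records: CR = n × p; usual care = n × p × c.
- With c = 0, P(CR count exceeds usual care) = 1 − (1 − p)^25.

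| p | c | Expected CR vs usual care | P(CR higher) |
|---|---|---|---|
| 2% | 0 | 0.5 vs 0 | 40% |
| 5% | 0 | 1.25 vs 0 | 72% |
| 10% | 0 | 2.5 vs 0 | 93% |
| 20% | 0 | 5 vs 0 | 99.6% |
| 10% | 0.5 | 2.5 vs 1.25 | 66% |
| 10% | 1 | 2.5 vs 2.5 | 40% (and 40% for the reverse) |

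A two-sided Fisher test at 0.05 on these counts would be significant in 3.3% of trials at p = 10%, c = 0, and in 38% at p = 20%, c = 0. No such test is planned. Swapping the capture fractions between arms swaps the counts, so the direction is not fixed. SAP section 4.1 describes 13 patients, or 6.5 per arm on average; p = 10% with c = 0 then gives 6.5 × 0.10 = 0.65 vs 0.

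**The case against.** A reader might infer that non-serious events are collected only if study-related at every step, that usual-care events are excluded by construction, and that the Aim 3 comparison is therefore broken. The documents do not support that reading.

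- Several steps carry no filter: sections 7.6, 10.1.1 and 12.5, the final EMR screen in 10.1, and the last line of 14.2.4. SAP sections 3.2 and 6.4 define S2 by the five events without a relatedness condition.
- The regimen wording in section 14.2.3 defines system-related events, whereas the form rule uses potentially study-related. The second term may be wider, and the word potentially sets a lower threshold than a final classification.
- Serious events of interest are recorded in both arms whatever their relatedness. ICD therapy should also be visible in the electrograms (section 12.5) and the remote interrogations (section 18.1), neither of which is restricted by arm.
- Usual care gets the same symptom-screening questions in the App (section 8.4.2).
- The event and capture rates in the illustration are assumed, and no planned inferential result is invalidated.

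All of this stands as a limit on the point. It does not remove it. The section devoted to AE reporting still states the narrower form rule, three other sections repeat its wording, and an ICD therapy visible in a device record is not thereby on an AE form.

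**Conclusion.** The protocol is internally contradictory on whether non-serious AEs are recorded regardless of relatedness. If the site applies the section 14.2.4 form rule, non-serious fracture and ICD therapy can be recorded unequally by arm, in either direction, and the Aim 3 listing would not be comparable between arms for those events. If the site applies section 10.1.1, the problem does not arise. Serious events of interest are unaffected under either rule.

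The size is unknown because the documents give no rates. The illustrated gap of 0.5 to 5 recorded events versus none is a worst case at 25 per arm. It rests on an assumed 2% to 20% risk and no usual-care capture. Nothing in the documents supports the upper end once the exposed set is narrowed to two event types. The point deserves correction because it affects the trial's only safety output and is cheap to close.

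**What to change.** Reconcile protocol sections 5.5, 10.1, 10.1.1, 10.1.2 and 14.2.4 so that relatedness is no longer a condition for collection. Suggested wording: all five events of special interest and all SAEs are recorded on an AE CRF in both arms, regardless of seriousness or relatedness; relatedness is assessed after recording. In section 14.2.3, state whether relatedness refers to the exercise regimen or to study participation, and use one term throughout.

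State that the EMR and device data named in section 12.5 are searched in the same way, over the same follow-up period, in both arms, and that any event of interest found there goes on an AE CRF. Ask both arms the same event questions in the App, with no judgement of relatedness by the patient. If enrolment has finished, the same two-arm search can still be run before the listing is produced.

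The cost is protocol and CRF wording plus a few more AE forms, probably mostly from usual care. The sources are already in the plan.

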#### 14.2.5 SERIOUS ADVERSE EVENT REPORTING

Regulatory reporting of AEs/device deficiencies will be completed according to local regulatory requirements. Refer to Table 4: SAE reporting timeframes for a list of required investigator reporting requirements and timeframes. The investigator is required to report all SAE's to the Sponsor immediately, and to the IRB per local requirements. The sponsor is also required to report these events to the local regulatory authority based on their requirements. It is the responsibility of the investigator to abide by any additional AE/device deficiency reporting requirements stipulated by the IRB responsible for oversight of the study. For AEs/device deficiencies that require immediate reporting, initial reporting may be done by contacting the study sponsor per the sponsor contact information provided in this document.

*Table 4: SAE reporting timeframes*

Serious Adverse Events	
Investigator submit to:	
Sponsor	Immediately
IRB	Per local IRB requirement
NESTcc	Immediately
Sponsor submit to:	
Regulatory authorities	Per local requirement
IRB	Per local IRB requirement

All SAEs will be followed and tracked until there is a satisfactory resolution or the site investigator uses their medical judgement to classify the participant as stable or suffering from a chronic illness.

According to 21 CFR 312.32(c)(2), “the FDA must be notified of any unexpected fatal or life-threatening suspected adverse reaction as soon as possible but in no case later than 7 calendar days after the sponsor's initial receipt of the information.”

#### 14.2.6 REPORTING OF EVENTS TO PARTICIPANTS

Due to the short timeline that we expect to use to enroll and complete the study, little time will be available to fully investigate suspected SAEs and AEs, however, if an AE or SAE does occur and it is determined to be related to study participation, subject participants who have not yet completed study procedures will be notified through the Pattern Health application. Contact information will be provided for additional details which will be provided by the study team through a scheduled phone call or letter.

## 15 RISK BENEFIT AND CONFIDENTIALITY

## 15.1 RISK/BENEFIT ASSESSMENT

Study subjects randomized to the intervention study arm will perform more PA than normal for the 12 weeks of study participation. During this time, they may be subject to increased risks of muscle or joint strain, fracture, fall, or soft tissue swelling or pain. Additionally, study subjects may have a higher risk of heart failure hospitalization, myocardial infarction, serious adverse arrhythmia, and ICD therapy. There are no expected long-term risks. Risks will be minimized by designing an exercise regimen that provides small incremental increases in physical activity and further increases will be guided by feedback provided by subjects through the Pattern Health application.

Participation in the research study may have potential benefit. Prior retrospective studies suggest that increased PA is associated with improved 1-5 year survival and reduced risk of hospitalization in patients who meet study inclusion criteria. Further work suggests that increased PA is also associated with reduced frequency and severity of depressive symptoms.

## 15.2 CONFIDENTIALITY AND MITIGATION PLAN

The Sponsor respects and protects personally identifiable information collected or maintained for this clinical investigation. The privacy of each subject and confidentiality of his/her information will be preserved in reports and when publishing any data. Confidentiality of data will be observed by all parties involved at all times throughout the clinical investigation. All data will be secured against unauthorized access.

All subjects will be provided with a subject identification number. A spreadsheet linking each subject ID to the patient's name and medical record number will be kept at the clinical site in a locked and encrypted file and will not be provided to the sponsor. All data transferred from the patient application will contain the subject ID number. Data will be stored in a REDCAP database and stored behind the Duke Firewall. The study PI, statistician, clinical research coordinators, and study coordinator will have access to the REDCAP database which will contain no PHI. Only the site PI and the site Clinical Research Coordinator will have access to the key linking the subject ID back to PHI.

The study database will be kept in a secure location for at least 5 years after study completion per IRB requirements.

## 16 RESULTS AND DISSEMINATION PLAN

The project team will publicly share the study design including the sources of study data and the method for linking the sources together for inclusion in the study database. This information will be included on clinicaltrials.org. Because the total study duration is expected to be short (with patient involvement lasting no more than 4 months) little time will be available to provide interim study updates.

The PI will be responsible for writing and submitting the scientific manuscript describing the results of the primary outcome. The PI may share responsibilities for publication of the secondary objective(s). The entire study team will be included as authors on publications. All co-authors will be provided access to the final results prior to manuscript publication. The study database will be stored in a repository at the Duke Clinical Research Institute after study completion. The study results will be made available to the study participants. If the active arm has improved outcomes relative to the controls, the controls will be offered participation in remote CR as part of their routine clinical care at Duke. This may not be directed by their implantable device PA data.

## 18 APPENDICES

### 18.1 PARTICIPANT SCHEDULE OF EVENTS

Table 5: Schedule of Events

	Screening / Baseline	Randomization	Initial Remote Physical Activity Session	Follow up Sessions	13 Weeks post Randomization (Completion)
Frequency	1	1	1	11	1
Type of Visit	Chart Review, Written Communication through EMR ± App ± Phone Call	Written Communication through App± Phone Call	Written Communication through App± Phone Call	Written Communication through App± Phone Call	Written Communication through App ± Phone Call
General eligibility criteria	•	•*			
Informed consent	•	•*			
Demographics	•				
Medical history	•	•*	•		
NYHA Assessment	•		•		•
KCCQ QoL Assessment			•		•
Remote Device Interrogation			•	•	•
Medication Review	•		•		•
Adverse Events			•	•	•
Weight, Blood Pressure, Glucose*	•			•	•
Patient Satisfaction Survey**					•

\*Diabetes Patients only

\*\*Remote Cardiac Rehab Patients only

### 18.2 LIST OF ABBREVIATIONS

ACC	American College of Cardiology
ACE-inhibitor	Angiotensin-Converting Enzyme inhibitor
AE	Adverse Event
AHA	American Heart Association
ANCOVA	Analysis of Covariance
ARNI	Angiotensin Receptor Neprilysin Inhibitor

BP	Blood Pressure
CFR	Code of Federal Regulations
CI	Confidence Interval
CIED	Cardiac Implantable Electronic Device
CIP	Clinical Investigative Plan
CMMS	Center for Medicare and Medicaid Services
CPET	Cardiopulmonary Exercise Test
CR	Cardiac Rehabilitation
CRF	Case Report Form
CRT	Cardiac Resynchronization Therapy
CRT-D	Cardiac Resynchronization Therapy Device
DCRI	Duke Clinical Research Institute
DOCR	Duke Office of Clinical Research
DSMB	Data Safety Monitoring Board
DUHS	Duke University Health System
ECG	Electrocardiogram
eCRF	Electronic Case Report Form
EDC	Electronic Data Capture
EMR	Electronic Medical Record
FDA	Food and Drug Administration
GCP	Good Clinical Practice
HF	Heart Failure
HIPAA	Health Insurance Portability and Accountability Act
ICD	Implantable cardioverter-defibrillator
ICF	Informed Consent Form
ICH	International Council for Harmonisation
IDE	Investigational Device Exemption
IND	Investigational New Drug
IRB	Institutional Review Board
ITT	Intention To Treat
KCCQ	Kansas City Cardiomyopathy Questionnaire
LVEF	Left Ventricular Ejection Fraction
MDIC	Medical Device Innovation Consortium
NESTcc	National Evaluation System for health Technology Coordinating Center
NIH	National Institutes of Health
NYHA	New York Heart Association
PA	Physical Activity
PHI	Protected Health Information
PHQ-9	Patient Health Questionnaire 9
PI	Principal Investigator
PP	Per Protocol
PRO	Patient-Reported Outcome
QOL	Quality of Life
SA	Safety Analysis
SAE	Serious Adverse Event
SAP	Statistical Analysis Plan

SD	Standard Deviation
US	United States

